### **Measuring gas flow:**

Maximum flow for this system is 19 L / min. The amount of gas flow is adjusted to match the patient's minute ventilation in order to maintain the black inspiration bag (inhalation reservoir) on the

Flowmeter about 3/4 full during the procedure. This varies from patient to patient depending upon respiratory rate, and volume of each breath. Excess gas flow simply flows through the circuit and into the scavenger and has no effect on the patient.

### **Periprocedural Data Collection**

After the biopsy, the patient will be moved to the recovery room for routine post-procedure vitals as well as completion of post-procedure STAI score and Situational Pain Catastrophizing Score (S-PCS) on a tablet computer. The S-PCS was derived from the Pain Catastrophizing Scale (PCS), a validated questionnaire used to measure catastrophic thinking associated with pain. We will also question for side effects of the nitrous oxide including nausea, vomiting, dizziness, drowsiness, with an option to enter “other” as a manual entry. An additional question of whether the patient feels comfortable driving home independently will be assessed.

Patients who do not have an escort planned after their biopsy will be asked to perform two hand-eye coordination tests after completion of post-procedure surveys. First, the participants will be verbally instructed to extend one arm in front of them, and place one finger to the tip of their nose. After, the Trail-making test Part B will be administered. This test has been promulgated by the American Medical Association to screen for driving fitness. The Trails-making Part B test will ask participants to connect numbers (1-13) to letters (A-L) randomly written on a page. This test is scored according to accuracy and time required to make the connections (Joseph, 2013). If the participant is unable to accurately complete these tests, additional recovery time will be required. The participant’s performance and disposition will be included in the documentation of study procedures performed during the visit.

The urologist who performed the biopsy procedure will be provided the Operator Survey to assess the ease of procedure.

Chart review will be performed to capture any unanticipated ED visits, admissions, or office visits for the 7 days following the procedure. We will also record any phone calls that are made by patients within 7 days of procedure that pertain to procedure concerns.

Lastly, participants who completed study procedures during their prostate biopsy will be asked to complete a survey 2-10 months following the study biopsy. This brief survey is designed to understand participant’s recollection of pain and anxiety during the biopsy. The survey is estimated to take 2-3 minutes to complete.

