### **Pre-procedure Evaluation**

On the day of the biopsy, current standard procedure is to bring the patient to an exam room (separate from the biopsy room) where pre-procedure vitals are obtained. At this time, the pre-procedure STAI and VAS scores will be obtained. Information of inhaled gas administration and how to self-administer will be explained to the patient using templated verbal instructions. It will be emphasized that if at any point during the procedure, the patient feels uncomfortable with the inhaled gas, the team will help remove the mask.

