### **Figure 1. Flowchart of Study Procedures**

### **Management of Medical Gases Used in Study**

As the research pharmacy does not procure nor dispense gaseous inhalants, medical gases used in the study will be managed per protocol and as per BIDMC's Compressed Gas Cylinder Storage and Handling Policy #: EC-62. Nitrous and oxygen cylinders will be procured through the OR materials management specialist. The tanks for study gases will be stored in an approved gas cylinder storage rack in (Room 385) of the Shapiro Clinic for immediate usage. There is also a gas tank

storage area in the Shapiro OR (close to the clinic) for additional storage. Both spaces are secured and locked off hours. Research staff will only access these supplies as necessary for the study.

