## B. Statistical Considerations

### Sample Size Justification

Based on a previous study by Bringman *et al*, the mean (SD) of STAI anxiety score is 34(8). A clinically meaningful decrease, as determined by the Cochrane review group was 0.5 of SD.

Our sample size calculation to detect a 4-point change in pain score (p less than 0.05 significance level) was 64 patients per group ( $\alpha=0.05$ , power=80%). We will inflate our sample size by 15% to account for any missing data or any withdrawal from the study; therefore, our estimated sample size will be 76 patients per group.

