### Data Analysis

All data will be collected and stored securely using the REDCap system. Data will be managed and analyzed by the PI and biostatistical support team at the BIDMC FIRST program. A Data Transfer Agreement will be created to allow for the study team's statistician, [name] MD/PhD at Brigham and Women's Hospital, to obtain and perform statistical analysis on de-identified data. At the conclusion of the study, de-identified study data will be exported out of REDCap and sent to [name] in a secure file via email message. Data will not be transferred until this agreement is approved and fully executed by both parties.

Primary outcome measure is patient anxiety and pain levels in the N2O group vs the oxygen only group as measured by the VAS and VAS A scores. We are specifically interested in the difference in scores between the two groups. Prostate biopsy mean VAS score with local anesthetic is around 3-4. We will also obtain a baseline pain index between the two groups. We will compare the perioperative VAS and VAS-A scores to the retrospective VAS and VAS-A scores collected during the survey administered 2-10 months after their biopsy.

We will also be obtaining 6 question Situational Pain Catastrophizing Scores for both groups and will compare the variation in response. Patients who have had a prior biopsy will also fill out a 13 question Pain catastrophizing score, which we will use as a baseline measure for biopsy related anxiety and hesitation.

Additional metric will include duration of biopsy, as measured by time in/time out of the procedure room for patients administered either nitrous or control oxygen when compared to patients who do not consent to the study (and will have no gas applied). Operator ease in performing the biopsy will be measured by 3 simple questions assessing patient positioning and ease of transrectal probe insertion. Prostate biopsies are generally performed as an outpatient procedure and patients can drive themselves home in most situations. Post biopsy side effects and ability of the patient to drive themselves home will be used as a surrogate to determine practicality of administering SANO in the outpatient setting.

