## **B7. STUDY LOCATION**

### **Privacy**

The study will be conducted on the premises of BIDMC Longwood Campus. We will obtain lists of patients intended for prostate biopsies in the following week, and study team members will review the OMR records for inclusion and exclusion criteria. The patient will be contacted by phone either from in-office phone call or through Doximity phone application (which provides the BIDMC Urology office as the caller ID). We will ask the patient whether they are in a location that affords privacy for discussion of medical information. If they are not, we will arrange an appropriate time when the patient will have privacy for study discussion. Phone interviews by study team members will be conducted in private space to avoid the interview being overheard.

Pre-procedure questionnaires will be emailed to private patient email via the REDCap server. Data collected will be kept within the REDCap server. Access to our REDCap will only be allowed for study team members who are trained in protecting PHI.

Operator Surveys will be on paper forms with patient identifying sticker on the form. At the end of the biopsy, the data will be input into the REDCap system by a study team member, and the paper version will be disposed of in a disposal unit intended for medical information waste.

Pre-procedure and post-procedure VAS, VAS-A score and Situational Pain Catastrophizing Score (S-PCS) and Trails-making Part B tests will be obtained in a private exam room where only the patient, study team members, and clinical staff measuring vitals will be present. Questionnaire answers will be input by the patient into a tablet computer. The tablet computer will be wiped with sanitizing wipe between uses given current COVID pandemic.

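### The declared primary outcome (VAS and VAS-A) is missing from the post-biopsy visit procedures, and the sample size was calculated for a different scale, the STAI

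*Combined protocol and SAP*

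**What the plan says.** The Data Analysis section (B3.B) names anxiety and pain as the primary outcome, "as measured by the VAS and VAS A scores". It does not mention STAI. VAS-A is not spelled out in the visible text; I take it to be the anxiety form of the visual analogue scale.

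The visit procedures in B3.A differ. Under Pre-procedure Evaluation, "the pre-procedure STAI and VAS scores will be obtained". Under Periprocedural Data Collection, the recovery-room step is "completion of post-procedure STAI score and Situational Pain Catastrophizing Score (S-PCS) on a tablet computer". Neither section lists VAS-A, and the second does not list VAS.

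The Privacy section (B7) gives another list: "Pre-procedure and post-procedure VAS, VAS-A score and Situational Pain Catastrophizing Score (S-PCS) and Trails-making Part B tests will be obtained", with "Questionnaire answers will be input by the patient into a tablet computer". STAI is not in that list.

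In the Specific Aims (B1), the anxiety hypothesis uses STAI, the situational pain catastrophizing scale and vital signs, and the pain hypothesis uses VAS and vital signs. The Sample Size Justification (B3.B) takes a mean of 34 and an SD of 8 for STAI from a published study and states: "A clinically meaningful decrease, as determined by the Cochrane review group was 0.5 of SD". It then describes the resulting 4 points as a change in a pain score, giving 64 per group at alpha 0.05 and 80% power, and 76 per group after a 15% allowance.

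**The concern.** Two things are at stake.

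The first is collection of the primary outcome. Staff who work from the two visit sections alone would record STAI and S-PCS after the biopsy, and no score on either declared primary scale. An on-day score that is missed cannot be recovered. The survey at 2–10 months measures recollection, and the Data Analysis section needs the on-day VAS and VAS-A as its comparator.

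The second is the basis of the sample size. The plan justifies its numbers by a 4-point difference on STAI, and then plans its primary comparison on VAS and VAS-A. The documents give no SD and no target difference for those two scales. The stated power therefore describes a comparison that the analysis section does not plan to make.

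**Working it through.** **1. The sections side by side**

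| Section | STAI | VAS | VAS-A |
|---|---|---|---|
| B1 Specific Aims | anxiety hypothesis | pain hypothesis | not named |
| B3.A Pre-procedure Evaluation | before | before | not named |
| B3.A Periprocedural Data Collection (on the day) | after | not named | not named |
| B3.B Sample Size Justification | mean 34, SD 8 | not named | not named |
| B3.B Data Analysis | not named | primary | primary |
| B7 Privacy | not named | before and after | before and after |

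Neither the visit sections nor the Privacy section alone covers every scale the plan relies on. The text does not show whether STAI and VAS-A are both to be given, or whether one was meant to replace the other.

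**2. Reproducing the plan's sample size**

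Inputs from the Sample Size Justification: SD 8, difference 0.5 × 8 = 4 points, alpha 0.05, power 80%. Allocation is 1:1 (Randomization). Sidedness is not stated, so two-sided is assumed.

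- Standardised difference: d = 4/8 = 0.5.
- Normal approximation: n = 2(1.96 + 0.842)²/0.5² = 62.8, so 63 per group.
- Two-sample t-test: n = 63.8, so 64 per group, with power 80.1% at 64. This is the plan's figure.
- One-sided alpha would give 50, which does not match.
- Allowance for loss: 64/(1 − 0.15) = 75.3, so 76 per group, or 152 in total. This also matches.

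The arithmetic is sound, and it is an STAI calculation.

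**3. Could the 4 points be VAS points?**

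The only VAS figure given is a mean of about 3–4 with local anesthetic. For an assumed SD of 1.5 to 3 in the same units, 4 points is 4/1.5 = 2.67 to 4/3 = 1.33 SD and needs only about 4 to 10 per group. On these assumptions 64 does not come from 4 VAS points, so pain score is a mislabel. For the same SDs, 0.5 SD on VAS is 0.75 to 1.5 points.

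**4. What 64 per group gives if VAS and VAS-A stay primary**

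Assume a true difference of 0.5 SD on each scale.

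- One scale, alpha 0.05: 80% power, because the calculation depends only on d.
- Both scales must succeed, each at alpha 0.05 (normal approximation): the expected test statistic is 0.5 × √(64/2) = 2.83, so the power for each is Φ(2.83 − 1.96) = 0.807. Jointly this is 0.807² = 0.65 at correlation 0, rising to 0.74 at correlation 0.8. The documents give no correlation, so this range is an assumption.
- Either scale may succeed, with alpha split to 0.025 each (t-test): 71% power for each. Reaching 80% for each would take 78 evaluable per group.

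**The case against.** The strongest reply is that the plan does declare its primary outcome and does provide for collecting it. Only the Data Analysis section uses the term, and it names VAS and VAS-A. The Specific Aims call nothing primary, and the Sample Size Justification only supplies planning inputs. The Privacy section says that VAS and VAS-A are obtained before and after the procedure, with answers entered on a tablet, and the Data Analysis section relies on perioperative VAS and VAS-A scores. A flowchart, "Figure 1. Flowchart of Study Procedures", is not visible here and may list every scale. The sample size also holds for any single scale at 0.5 SD.

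Much of this stands. A reader might infer that on-day VAS and VAS-A will not be collected. The documents do not support that, because two sections plan for those scores. A reader might also infer that the primary scale is undeclared, and that choosing between STAI and VAS-A after seeing results would inflate the false-positive rate. That would require the sponsor to set aside its own declaration, which nothing in the documents suggests, and any figure for the inflation would rest on a correlation they do not give.

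The reply does not remove the mismatch. The visit sections are the procedural instructions, and they omit the primary scales after the biopsy. A flowchart could settle the schedule, but it could not turn a sample size based on STAI into one for VAS and VAS-A. The power reassurance also covers one scale, whereas the plan declares two and gives no rule for success.

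**Conclusion.** The point holds as an inconsistency between the declared primary outcome, the visit procedures and the sample-size basis. Loss of the on-day primary outcome is a risk; how large it is cannot be judged without Figure 1 and the tablet form. The 64 and 76 per group are correctly computed, but for STAI, so the 4-point, 80%-power statement cannot be carried over to VAS and VAS-A. A reader might go further and call the trial underpowered. That does not follow: at 0.5 SD the power is 80% for a single primary scale, and falls to about 65–74% or 71% only if two primaries are kept under the rules shown. Those figures assume 0.5 SD on each scale, 64 evaluable per group and, for the joint figure, a correlation of 0 to 0.8.

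This should be corrected before data are seen, because a missed on-day score cannot be replaced and the correction is cheap.

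**What to change.** **Primary outcome and sample size.** Before data are seen, reconcile the Specific Aims, Sample Size Justification and Data Analysis sections so that the declared primary scale or scales, and the time point, are also those of the sample size. The choice is the sponsor's.

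- If post-procedure STAI is made primary, 64 per group stands. Change pain score to STAI score, add a between-group STAI comparison to Data Analysis, and record the change of primary outcome as an amendment.
- If VAS and VAS-A stay primary, restate the justification for them at 0.5 SD instead of 4 points, and align the anxiety hypothesis. Then either name one scale as primary or state the rule for two, and give the power under that rule in place of 80%.

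**Schedule.** List every scale declared primary, both before and after the biopsy, under Pre-procedure Evaluation and Periprocedural Data Collection. Make the Privacy section, Figure 1 and the tablet form agree. List STAI or VAS-A elsewhere only if the sponsor confirms that it is still to be given.

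**Cost.** Protocol wording and a check of the tablet form. The stated power may become less favourable if two primaries are kept. Extra patients would be needed only if the sponsor wanted to restore 80% power in that case.

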#### Specific Aims:

**Aim 1:** To determine the effectiveness of Self-Administered Nitrous Oxide (SANO) in decreasing patient perceived anxiety and pain related to prostate needle biopsy.

*Hypothesis 1.1: Patients receiving periprocedural SANO will have decreased anxiety during the procedure, as measured by STAI (State-Trait Anxiety Inventory) score, situational pain catastrophizing scale (SPCS) and patient vital signs.*

*Hypothesis 1.2: Patients receiving periprocedural SANO may have a decrease in pain as measured by VAS (visual analogue scale) score and patient vital signs.*

**Aim 2:** To demonstrate that the SANO at the time of prostate biopsy does not significantly increase burden on Urologist productivity, nor increase the difficulty of performing the biopsy.

*Hypothesis 1.1: Administration of periprocedural SANO will not significantly lengthen the time of the procedure relative to local anesthetic alone.*

*Hypothesis 1.2: Administration of periprocedural SANO will result in minimal side effects for the patients and will allow the patient to drive home independently.*

*Hypothesis 1.3: Administration of periprocedural SANO will allow the operating Urologist to perform the procedure with the same ease as on those patients who do not have SANO.*

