##### Risks related to Nitrous Oxide administration

Nitrous oxide is a well-known drug used in medicine for anesthetic and analgesic purposes since 1844. Its use during labor has been shown to be safe and effective, with no known long-term effects on the mother and no known effects on the infant. There are known long-term effects of environmental exposure to nitrous oxide, including infertility, when not using a scavenger system for the escaped environmental nitrous oxide. The Miniscav® nitrous waste gas evacuation pump has been FDA-approved for use in medical offices with the Nitrouseal® system. We will not be using the Nitrouseal® and Miniscav® nitrous waste gas evacuation pump in any capacity that is not already approved by the FDA.

Nitrous oxide does have a risk of nausea and vomiting. The reported rates have been reported as high as 13% in literature, however these are at higher concentration of nitrous oxide and with longer durations. The reported vomiting risk with the Nitrouseal® system is <0.5%. For the procedure, the patient is maintained in the lateral position, which should minimize any aspiration risk. Sweating, drowsiness, lightheadedness, tachycardia and facial flushing has also been reported. The patients are routinely monitored after the prostate biopsy procedure, and any ill effects of the procedure itself or of the nitrous oxide will be assessed and cared for by our study team and clinical staff. Some adults may feel a sense of panic at higher concentrations (60-70%) than we will be using in our study (40%).

Finally, as with any inhaled gas, there can be a concern of hypoxia or apnea with administration of nitrous oxide. This event has not been routinely reported in the literature as a risk or side effect of nitrous oxide. However, this will be one of the side effects that we will be most interested in following. During the procedure, patients will undergo continuous oxygen saturation and heart rate monitoring. These values will be documented in REDCap as part of the patient's study records.

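### The side-effect questions give no prompt for sweating and facial flushing, which the plan's own risk section reports, and do not say that the oxygen arm is asked the same questions (low priority)

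*Combined protocol and SAP*

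**What the plan says.** Periprocedural Data Collection (B3.A) describes the post-procedure questioning in the recovery room: "We will also question for side effects of the nitrous oxide including nausea, vomiting, dizziness, drowsiness, with an option to enter" other effects by hand. Four symptoms are therefore named and the rest depend on a volunteered entry. The same section adds a question on driving home, a 7-day chart review for unplanned visits and admissions, and a record of patients' phone calls.

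Risks related to Nitrous Oxide administration (B5) is broader. It says "Nitrous oxide does have a risk of nausea and vomiting", then "Sweating, drowsiness, lightheadedness, tachycardia and facial flushing has also been reported". It adds that "Some adults may feel a sense of panic at higher concentrations", which it places at 60-70%, above the 40% it gives for this study. It also says "there can be a concern of hypoxia or apnea with administration of nitrous oxide", and provides for continuous oxygen saturation and heart rate monitoring with the values entered in REDCap.

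The Purpose of Protocol (B1) names the frequency of SANO complications as one thing the trial will assess. Hypothesis 1.2 under Aim 2 is that SANO "will result in minimal side effects for the patients". Data Analysis (B3.B) makes anxiety and pain the primary outcome and uses side effects as a surrogate for outpatient practicality.

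**The concern.** A symptom that is asked about by name will generally be reported more often than one the patient must think to volunteer. If the plan's own list of known effects is longer than its list of questions, the unlisted effects are measured less well. An effect that goes unrecorded makes a conclusion of few side effects easier to reach.

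Timing adds to this. The background section puts both onset and elimination of nitrous oxide at 2-3 minutes, and Periprocedural Intervention gives a further 2-3 minutes of oxygen before the patient leaves the biopsy room. By the time of questioning, a flush or sweat felt under the mask may have passed, so its record depends on recall.

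The second issue is the comparison. Periprocedural Intervention says explicitly that both groups get the questions on the level of gas. Periprocedural Data Collection says nothing similar for the side-effect questions, and words them as effects of nitrous oxide although patients are blinded. Without an oxygen-arm rate from the same questions, symptoms caused by the biopsy cannot be separated from those caused by the gas.

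**Working it through.** **1. The plan's own design figure.** The only design calculation is for the score outcome: a difference of 4 with SD 8, alpha 0.05, power 80%. The two-sample t-test (two-sided) gives 63.77, so 64 per group. Inflation for 15% loss gives 64 / (1 - 0.15) = 75.3, so 76 per group. Both stated figures reproduce. Neither depends on the side-effect list.

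**2. The two lists side by side.**

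| Effect named in B5 | How the plan captures it |
|---|---|
| Nausea | Prompted |
| Vomiting | Prompted |
| Drowsiness | Prompted |
| Lightheadedness | Reasonably covered by the dizziness prompt |
| Tachycardia | Heart rate monitored, values in REDCap |
| Hypoxia | Oxygen saturation monitored, values in REDCap |
| Apnea | Indirectly, through saturation and the bedside observer |
| Sweating | Free text only |
| Facial flushing | Free text only |
| Panic | Free text only, but tied in B5 to 60-70% |

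The clear remainder is sweating and facial flushing.

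**3. Could another route record them?** Chart review and phone calls detect contacts with the clinic over 7 days, not a symptom lasting minutes. Saturation and heart rate do not measure sweating or flushing. Adverse event reporting passes on what has been noticed but does not ask for it.

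**4. Panic and mask distress.** B5 gives 40% for this study and Periprocedural Intervention gives a range of 25-45%. The two should be reconciled, but both lie below 60-70%, so B5 does not present panic as expected here. However, Pre-procedure Evaluation and Periprocedural Intervention both foresee a patient who dislikes the gas and has the mask removed. Neither says that this event or its reason is recorded.

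**5. Size, by assumption only.** The documents give neither the rate of sweating or flushing nor the share that free text would catch. Let N = 76 SANO patients, p the true rate of an unprompted effect and s the share caught. Expected recorded = N × p × s, and P(none recorded) = (1 - p × s)^76.

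| p | s | True expected | Recorded expected | P(none recorded) |
|---|---|---|---|---|
| 5% | 100% | 3.8 | 3.8 | 2.0% |
| 5% | 75% | 3.8 | 2.85 | 5.5% |
| 5% | 50% | 3.8 | 1.9 | 15% |
| 5% | 25% | 3.8 | 0.95 | 38% |
| 2% | 50% | 1.52 | 0.76 | 47% |
| 10% | 50% | 7.6 | 3.8 | 2.0% |

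**6. Direction.** If both arms use the same form and s is equal, the recorded difference is s × (p_SANO - p_oxygen). With assumed rates of 10% and 2% and s = 50%, the arms record 5% and 1%. The difference falls from 8 to 4 percentage points and the ratio stays at 5. If the oxygen arm is not asked, there is no comparison, and biopsy symptoms may be counted against the gas. That error would run the other way.

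**The case against.** The strongest reply is that the gap is small. Most of the effects in B5 are prompted or monitored, and the use Data Analysis makes of side effects is practicality and driving home. Drowsiness and dizziness matter more for that than sweating or flushing. The word introducing the list may mean that it is not exhaustive, and the form itself is not in the documents. All of this stands and is why the priority is low. It does not remove the point: a free-text option after four named symptoms reads as a fixed list, and the frequency of complications is a stated purpose of the trial.

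A reader might infer more than the documents support:

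- *That complication frequency is undercounted.* This is a risk. The rates in the tables above are assumed, and with equal capture in both arms the main effect is a smaller absolute difference.
- *That panic is a known effect left off the form.* B5 ties it to concentrations above those planned. Anxiety is also measured after the procedure in both arms, by STAI (VAS-A in the Privacy section) and the situational catastrophizing score, although none of these is a panic item.
- *That the quoted vomiting rate below 0.5% cannot be confirmed with 76 patients.* Vomiting is prompted, so this has no bearing on the checklist, and the plan does not claim to confirm that rate.
- *That side effects are what the trial mainly exists to report.* They are one purpose. Anxiety and pain are primary.

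**Conclusion.** The point holds as a minor weakness in data collection. Two effects that the plan itself reports with nitrous oxide, sweating and facial flushing, rely on free text and are at risk of under-recording. The plan does not say that the oxygen arm is asked the same questions, and their wording presumes nitrous oxide. Mask removal for discomfort is foreseen but nowhere said to be recorded.

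This rests on reading the four named symptoms as the full set of prompts and on prompted symptoms being reported more fully than volunteered ones. The amount of under-recording cannot be derived from the documents, and the figures above only illustrate a range. The sample size of 76 per group and the primary analysis are unaffected. Low priority.

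**What to change.** In Periprocedural Data Collection, add sweating and facial flushing as yes/no items beside the existing four, keeping the free-text option. Optionally add one item on distress with the mask or gas, which would also register discomfort leading to mask removal.

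Reword the stem neutrally, for example: symptoms during or after the procedure. State that both arms answer the identical items, on the tablet already used for the post-procedure questionnaires.

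In Data Analysis, add one sentence: each item is reported as a rate by arm, with the SANO minus oxygen difference and exact 95% confidence intervals.

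The cost is two or three tick boxes, a reworded stem and one sentence of analysis. The recorded side-effect profile may look less favourable than with the four-symptom list. New items help only from the date they are introduced, so the change is worth making early.

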### **Randomization**

Subjects will be randomized 1:1 to either SANO (treatment) or oxygen (placebo control) after completion of baseline assessment. The results of the randomization will not be disclosed to patients as part of the study (patient-blinded). The randomization module in REDCap will be used to implement randomization of the subject to our two study groups.

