### **Periprocedural Intervention**

The patient will be moved to the biopsy room and standard procedure for lateral positioning and explaining prostate biopsy will be done in the routine manner preferred by the individual Urologist. Oxygen saturation monitor will be applied to the patient's finger and monitored throughout the procedure. The patient's heart rate will also be monitored accordingly.

The inhalation gas mask will be positioned on the patient's face, and the patient will then be instructed to begin breathing as previously instructed. Initially the patient will receive 100% oxygen at 10 Liters/minute. In the control group, this will be continued throughout the procedure.

After the Urologist describes the procedure, the SANO group will have nitrous oxide turned on to 30%, ensuring that the patient is relaxed but still conversant through the procedure. The nitrous will be adjust up or down based on the patient's response to the question "are you feeling the nitrous" and "are you happy at this level". The range will be between 25 - 45%. This may take 2-3 minutes. Both groups will be asked these questions. Both groups will be asked to take several deep breaths before inserting the rectal probe. The prostate biopsy for both study and control participants will include the normal routine administration of local peri-prostatic nerve block using preferred technique of the individual Urologist. During the procedure, the patient and patient's oxygen saturation will be monitored by a [name], APP, or MD (separate from MD performing the procedure) and if at any point in time the patient is unhappy with gas inhalation, the observer will aid the patient in removing the mask. At the end of the procedure, the SANO group will be turned down to 0% nitrous oxide, and 100% oxygen will be administered through the mask for an additional 2-3 minutes as the patient is cleaned up and repositioned to the supine position. Assessment of the "time in" and "time out" of the procedure room will be recorded.

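### Only patients are blinded, so the urologist's own rating of ease, on which the 'same ease' hypothesis rests, is open to a rating bias that could be reduced, though not removed

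*Combined protocol and SAP*

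**What the plan says.** All references are to the combined protocol and SAP.

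- **Who is blinded.** B3.A, Randomization: "The results of the randomization will not be disclosed to patients as part of the study (patient-blinded". No section extends blinding to the operating urologist, the observer or the staff who collect the recovery-room surveys.
- **Who rates.** B3.A, Periprocedural Data Collection: "The urologist who performed the biopsy procedure will be provided the Operator Survey to assess the ease of procedure".
- **What is rated.** B3.B, Data Analysis: "Operator ease in performing the biopsy will be measured by 3 simple questions assessing patient positioning and ease of transrectal probe insertion". No response scale, scoring rule or analysis is given.
- **What it is for.** B1, Specific Aims, Aim 2, Hypothesis 1.3: SANO will allow the urologist to "perform the procedure with the same ease as on those patients who do not have SANO". No equivalence or non-inferiority margin accompanies it.
- **Who runs the gas.** B3.A, Periprocedural Intervention, uses the passive: "the SANO group will have nitrous oxide turned on to 30" per cent, and "The nitrous will be adjust up or down based on the patient's response to the question". Nobody is named.
- **Who else is in the room.** The same section requires an observer who is "separate from MD performing the procedure". That person's stated tasks are to watch the patient and the oxygen saturation and to help take off the mask.

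**The concern.** A three-item rating of positioning and probe insertion is a judgement, and the person making it is not described as masked. The expected result is no difference. A rater who knows the arm and is inclined to favour SANO would pull the scores towards that result, and with no margin stated, a null finding could be read as support for it. A rater who dislikes working around the gas could do the opposite and create a difference that is not there.

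The gap is worth closing because much of the masking is already built in. Both arms wear the mask, start on oxygen alone, are asked the same two questions about the gas, and take deep breaths before the probe is inserted. What is missing is any statement that the operator is not told the arm and cannot read the setting.

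**Working it through.** **1. The plan's own figure.** B3.B, Sample Size Justification, gives SD 8, a difference of 4 (0.5 SD), alpha 0.05 and power 80%. The test's sidedness is not stated; two-sided reproduces the result.

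- Normal approximation: n = 2 × (1.960 + 0.842)² × (8/4)² = 62.8, so 63 per arm. The two-sample t-test gives 63.8, so 64, as stated.
- Allowance for loss: 64/0.85 = 75.3, so 76 per arm and 152 in total, as stated.

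This calculation is for an anxiety score. The documents give no size, SD or power for operator ease, so 64 and 76 are used below only as the numbers of patients available.

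**2. Leniency hiding a real loss of ease (illustration).** Two quantities are assumed because the documents give neither: a true loss of ease of 0.5 SD under SANO, and a leniency b, in SD units, towards SANO. The visible difference is d = 0.5 − b. Power is that of a two-sided 5% two-sample t-test with noncentrality d × √(n/2), where √(64/2) = 5.657 and √(76/2) = 6.164.

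| Leniency b (SD) | Visible d (SD) | Power, 64 per arm | Power, 76 per arm |
|---|---|---|---|
| 0 | 0.50 | 80% | 86% |
| 0.05 | 0.45 | 71% | 79% |
| 0.10 | 0.40 | 61% | 69% |
| 0.20 | 0.30 | 39% | 45% |
| 0.25 | 0.25 | 29% | 33% |

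For the last row, the noncentrality is 0.25 × 5.657 = 1.41 at 64 per arm and 0.25 × 6.164 = 1.54 at 76.

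**3. Bias creating a difference (illustration).** If ease is truly equal, a pure rating bias of 0.10, 0.20 or 0.25 SD in either direction gives a significant result in about 9%, 20% or 29% of trials at 64 per arm, and 9%, 23% or 33% at 76. The nominal rate is 5%.

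**4. What the text settles about masking.** The Randomization section withholds the allocation from patients only. Periprocedural Intervention places a second person in the room but gives that person observation and mask removal, and leaves the flowmeter unassigned. So the text neither gives the operator the allocation nor keeps it from the operator.

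**The case against.** The strongest reply is that masking the operator would achieve little. The gas is adjusted over two to three minutes from the patient's spoken answers, and the plan expects a relaxed patient who can still converse. A urologist in the room can hear those answers and see the effect, and turning a display away does not remove such cues. This stands: the bias can be reduced, not eliminated.

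A reader might also infer four stronger points that the documents do not support.

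- *That a separate person already runs the gas, so the bias is avoidable at no cost.* The plan gives the observer other tasks and never says who operates the flowmeter.
- *That the operator certainly knows the arm.* This is read from blinding being described for patients alone and from silence elsewhere. It is a fair reading, because nothing prevents the knowledge, but it is not stated.
- *That the patient-reported pain and anxiety scores are compromised too.* An operator who knows the arm might behave differently, but no passage shows it. Patients are blinded, receive templated gas instructions and enter their own answers on a tablet, and the urologist describes the procedure before nitrous oxide is turned on. The pathway is speculative.
- *That a real burden would be reported as equal ease.* No analysis of operator ease is specified. In the 0.5 SD illustration, 20% of trials at 64 per arm miss the effect even without bias.

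The power figures are also open to challenge, since a three-question measure with no stated scale gives SD units no anchor. They show sensitivity over a range and do not estimate the bias in this trial.

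**Conclusion.** The point holds as a limited one. The plan describes blinding for patients only, leaves the running of the gas unassigned, and has the operating urologist give a subjective rating for a hypothesis of no difference. That comparison is open to rating bias in either direction. Under the assumed 0.5 SD loss of ease, even 0.10 SD of leniency would lower power by about 19 percentage points at 64 per arm (80% to 61%) and 17 at 76 (86% to 69%). The size of any actual bias is unknown.

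The consequence is confined to a secondary aim and does not touch the sample size. It is an inexpensive improvement, and the trial does not depend on it.

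**What to change.** 1. In B3.A, Randomization and Periprocedural Intervention, state that the operating urologist and the recovery-room survey staff are not told the arm.
2. State who runs the gas. Where feasible, let the observer already required handle the flowmeter, or whoever runs it now if that is not the operator, with the display turned away from the operator.
3. State that masking does not limit the response to suspected hypoxia already set out in B5, Risks related to Nitrous Oxide administration.
4. Add 'which gas do you think was given?' as the last item of the Operator Survey, and report the guesses by arm beside the ease ratings. This shows how far masking worked.
5. If shielding is not workable, report operator ease as an unblinded rating and word the conclusion on Hypothesis 1.3 accordingly.

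The cost is protocol wording, room set-up and one survey question. Two limits remain: patient behaviour may still give the arm away, and the sponsor must confirm that the observer can take on the flowmeter without added staff.
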